6. GENERAL CONSIDERATIONS

The following descriptive statistics will be presented in summary tables:

- Continuous variables: number (valid cases), mean, median, standard deviation (SD), minimum, and maximum
- Categorical variables: summarized by treatment group using frequency tables (frequencies and percentages). Percentages are routinely based on the total within the group count excluding the

Document:	CCI	Version Number:	1.0
Author:	PPD	Version Date:	06 Oct 2017
Template No:	CCI	Reference:	CCI
Effective Date:	01Apr2016		

missing category if not otherwise mentioned. Missing category with zero count will not be presented.

In general, the number of decimal places displayed for each statistic will be determined as follows:

- Mean and median: 1 more than the number of decimal places allotted in the raw data received from data management.
- SD: 2 more than the number of decimal places allotted in the raw data.
- Minimum and maximum: equal to the number of decimal places allotted in the raw data.
- Percentages: All percentages between 0% and 100% will be rounded to one decimal unless there is a need to report more than one decimal for percentages.
- Ranges will be reported to the same number of decimal places displayed by the laboratory.

6.1. REFERENCE START DATE AND STUDY DAY

Reference start date is defined as the day of the first dose of study medication, (Day 1 is the day of the first dose of study medication), and will appear in every listing where an assessment date or event date appears. If Reference Start Date < Date of randomization, it will be considered as protocol deviation and detailed accordingly in the PD Log.

Study Day will be calculated from the reference start date, and will be used to show start/ stop day of assessments and events.

- If the date of the event is on or after the reference date then:
Study Day = (date of event – reference date) + 1.
- If the date of the event is prior to the reference date then:
Study Day = (date of event – reference date).

In the situation where the event date is partial or missing, Study Day, and any corresponding durations will appear partial or missing in the listings.

6.2. PRECISION

Safety variables (i.e. clinical laboratory values, vital signs, and ECG intervals), including derivations thereof will be reported to the same precision as the source data.

All PK and PD concentrations will be reported and analysed with the same precision as the source data provided by the bio-analytical laboratory or clinical laboratory regardless of how many significant figures or decimals the data carry. Time variables for PK/PD will have units of hour and have two decimal places, for source data used for calculation of PK/PD parameters, and for reporting in listings. Derived PK parameters will be rounded for reporting purposes in by-subject listings. The rounded derived PK parameter values in listings will be considered the source data for the calculation of descriptive statistics. For most derived PK/PD parameters, 3 significant digits will be used as the standard rounding procedure, with the following exceptions:

Document:	CCI	Version Number:	1.0
Author:	PPD	Version Date:	06 Oct 2017
Template No:	CCI	Reference:	CCI
Effective Date:	01Apr2016		

- Parameters directly derived from source data (e.g. C_{max}) will be reported and analysed with the same precision as the source data.
- Parameters derived from actual elapsed sample collection times (e.g., t_{max}) will be reported with the same precision as the actual elapsed sampling time value of the source data, normally 2 decimal places.

For the reporting of descriptive statistics, the mean will be presented to one digit more precision than the source data. Standard deviation will be presented to two digits more precision than the source data. The minimum, median, and maximum, will be presented to the same precision as the source data. Coefficient of variation and percentages will always be reported to 1 decimal place.

6.3. BASELINE

Unless otherwise specified, baseline is defined as the last non-missing measurement (including unscheduled assessments) taken prior to the reference start date and/or time. If the last non-missing measurement is recorded on the day of IP administration and is specified to be done pre-dose as per the protocol then it will be considered baseline. For Adverse Events/Concomitant Medications if start date and/or time of measurement and IP administration coincide, that measurement will be considered as post-baseline.

6.4. UNSCHEDULED VISITS AND EARLY TERMINATION DATA

In general, for by-visit summaries, data recorded at the nominal visit (including optional visits) will be presented. Unscheduled measurements will not be included in by-visit summaries and efficacy analyses. Early termination data will be mapped to the next available visit number for by-visit summaries. Listings will include scheduled, unscheduled, retest and early termination data.

6.5. WINDOWING CONVENTIONS

No visit windowing will be performed for this study.

6.6. STATISTICAL TESTS

The default significance level will be (5%); confidence intervals will be 95% and all tests will be two-sided, unless otherwise specified in the description of the analyses.

6.7. COMMON CALCULATIONS

For quantitative measurements, change from baseline will be calculated as:

Document:	CCI	Version Number:	1.0
Author:	PPD	Version Date:	06 Oct 2017
Template No:	CCI	Reference:	CCI
Effective Date:	01Apr2016		

- Test Value at Visit X – Baseline Value

6.8. SOFTWARE VERSION

For tables, listings and graphs SAS ® version 9.4 will be used.

Non-compartmental PK parameter calculations will be performed using Phoenix® WinNonlin® 6.4 or higher (Certera, Princeton, New Jersey).

Figures may be prepared using SAS®, Phoenix® WinNonlin®, or SigmaPlot 12.5 or higher (Systat Software, Inc., San Jose, California, United States).

7. STATISTICAL CONSIDERATIONS

7.1. ADJUSTMENTS FOR COVARIATES AND FACTORS TO BE INCLUDED IN ANALYSES

Baseline will be used as covariate in all analyses of change from baseline MG data. Wherever appropriate baseline x visit term will be included in the analysis. In case of non-convergence, baseline*visit term will be excluded from the model and/or an appropriate covariance matrix will be used.

7.2. MULTICENTER STUDIES

This study will be conducted by multiple investigators at multiple sites. However, because of the small sample size (12 subjects planned per treatment group) analysis models will not include the factor center.

7.3. MISSING DATA

Missing safety and efficacy data will not be imputed. For efficacy data the missing data handling approach will be based on MMRM.

7.4. MULTIPLE COMPARISONS/ MULTIPLICITY

No adjustment is made for multiplicity since this is an exploratory study and no confirmatory hypothesis testing is performed.

7.5. EXAMINATION OF SUBGROUPS

No subgroup analyses will be performed for this study.

Document:

CCI

Author:

PPD

Version Number:

1.0

Version Date:

06 Oct 2017

Template No: CCI

Effective Date: 01Apr2016

Reference: CCI

Copyright © 2009, 2010, 2012, 2016 Quintiles Transnational Corp. All rights reserved.

The contents of this document are confidential and proprietary to Quintiles Transnational Corp. Unauthorized use, disclosure or reproduction is strictly prohibited.

8. OUTPUT PRESENTATIONS

The Mock Shells provided with this SAP describe the format, layout and content of the summary tables, figures and listings to be provided by QuintilesIMS Biostatistics. This document will be a working document and updates will be documented in its modification history.

All visit assessments will be presented according to the nominal visit name. Study populations will be summarized and listed as well.

9. DISPOSITION AND WITHDRAWALS

All subjects who provide informed consent will be accounted for in this study.

Data collected on Early Termination (ET) and End of Study (EOS) in the electronic Case Report Form (eCRF) will be used to present disposition and withdrawal results. Frequency tables will be provided for:

- number of subjects who provided informed consent
- number of subjects randomized
- number of subjects treated with at least one dose of study medication
- number of subjects who completed the treatment period with minimum of 2 weeks FU
- number of subjects who completed the study
- number of subjects still ongoing in the study
- number of subjects who discontinued the study
- primary reason for discontinuation of the study
- number of subjects who discontinued the treatment
- primary reason for treatment discontinuation

A listing will be presented of dates of Screening, randomization, screen failure with reason, completion or early discontinuation/withdrawal and the reason for early discontinuation, if applicable, for each subject.

10. PROTOCOL DEVIATION

All protocol deviations/violations observed during study conduct will be captured in Clinical Trial Management System (CTMS).

QuintilesIMS and sponsor will review the protocol deviation records from CTMS and provide confirmation of the categorization of deviations as minor, major or critical.

A frequency table for major protocol deviations will be provided. The listing of all protocol deviations will be presented.

Document:	CCI	Version Number:	1.0
Author:	PPD	Version Date:	06 Oct 2017
Template No:	CCI	Reference:	CCI
Effective Date:	01Apr2016		

11. DEMOGRAPHIC AND OTHER BASELINE CHARACTERISTICS

Demographic data and other baseline characteristics will be presented for the Randomized population.

The Summary statistics will be provided for:

- Age (years)
- Weight (kg)
- Height (cm)
- BMI (kg/m²)

Frequency tables will be provided for:

- Sex
- Ethnicity
- Race

A listing for subject demographic data and other baseline characteristics; including Weight, Height and BMI will be presented.

12. MEDICAL HISTORY

Medical History will be presented for the Safety population and coded using Medical Dictionary for Regulatory Activities (MedDRA) coding dictionary version 19.1. Medical History conditions are defined as those conditions which stop prior to or at Screening.

Frequency tables (presented by System Organ Class (SOC) and Preferred Term (PT) and Listings will be provided for the Safety Population. Myasthenia Gravis History including information about MGFA classification, anti-AChR antibodies testing, neuromuscular transmission test, edrophonium chloride test and improvement on MG signs on oral cholinesterase will be listed and summarized for the Safety Population.

13. CONCOMITANT MEDICATIONS

Prior and concomitant medications will be presented for the Safety Analysis Set. A frequency table will be provided for all medications by Anatomic, therapeutic and chemical classification (ATC) Level 1 and 3. A separate frequency table will be provided for Myasthenia Gravis therapy medications. All medications will be coded by the WHO Drug Dictionary version Dec 2016.

See Appendix 1 for handling of partial dates for medications. If it is not possible to define a medication as either prior or concomitant, the medication will be classified by the worst case; i.e. concomitant.

- 'Prior' medications are medications which started and stopped prior to the first dose of study medication.
- 'Concomitant' medications are medications which:
 - o started prior to, on or after the first dose of study medication

Document:

CCI

Author:

PPD

Version Number:

1.0

Version Date:

06 Oct 2017

Template No: CCI

Effective Date: 01Apr2016

Reference: CCI

- o AND ended on or after the date of first dose of study medication or were ongoing at the end of the study.

Listings of medications and of MG therapy given to subjects with all details will be presented.

14. STUDY MEDICATION EXPOSURE

Study medication exposure will be presented for the Safety Analysis Set. A listing of exposure to study medication in days will be presented along with details of start and end time of infusion, interruptions, total volume administered, prematurely stopped and whether subject remained at the site for 2 hours after end of infusion. A summary of exposure to report the number of completed infusions and a separate listing to show any overdoses will be presented.

15. EFFICACY OUTCOMES

All efficacy analysis will be performed using FAS. The following summaries and corresponding listings will be provided for the efficacy results:

- Summary of scores and change from baseline by visit, at each post baseline visit for
 - Myasthenia Gravis-Activities of Daily Living (MG-ADL) score
 - Quantitative-Myasthenia Gravis score (QMG)
 - Myasthenia Gravis Composite score (MGC)
 - Quality of life using 15-item quality of life scale for Myasthenia Gravis (MGQoL15r [revised version])
- Maximum reduction in score from baseline across visit days for MG-ADL, QMG, MGC, and MGQoL15r score.

The analyses of data derived from the various scales (MG-ADL, QMG, MGC, and MGQoL15r) will be based on the FAS. Actual score, change from Baseline and maximum reduction from Baseline will be summarized descriptively.

Analyses of change from baseline by visit will be performed using a mixed-model repeated measures (MMRM) analysis from Visit 1 to Visit 16. The model will include treatment, visit and treatment x visit interaction terms as fixed effects, with baseline and baseline x visit terms as covariates. If the baseline x visit term is found to be not significant then it can be excluded from the model. An unstructured (UN) covariance matrix for the repeated measures within subject will be specified for the analysis* and the following statistics will be presented for each visit:

- Least Square (LS) Means per treatment group
- Standard error of LS Means
- 95% confidence interval (CI)
- LS Mean Difference (ARGX-113 – Placebo)
- Standard error of LS Mean Difference

Document:

CCI

Author:

PPD

Version Number:

1.0

Version Date:

06 Oct 2017

Template No: CCI

Reference: CCI

Effective Date: 01Apr2016

Copyright © 2009, 2010, 2012, 2016 Quintiles Transnational Corp. All rights reserved.

The contents of this document are confidential and proprietary to Quintiles Transnational Corp. Unauthorized use, disclosure or reproduction is strictly prohibited.

- 95% confidence interval (CI) for LS Mean Difference
- p-value for testing differences between treatment groups

*If the model does not converge upon using UN, a simpler covariance matrix like CSH (not restrictive) will be used instead.

A box plot for change from baseline of ARGX and Placebo will be presented across visits. A box plot also presented for maximum reduction from baseline score.

Analysis of maximum reduction in scores will be performed using ANCOVA with baseline score as a covariate and treatment as fixed factor.

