4.2 Secondary Endpoints

- Score change from Baseline (defined as the score immediately prior to first dose at Visit 1) at Visits 3, 5, 7, 9, 10, 11, 12, 14, and 16 for the following:
 - MG-ADL
 - QMG
 - MGC
 - MGQoL15r
- Maximum reduction from Baseline across visit days for MG-ADL, QMG, MGC, and MGQoL15r score.
- Pharmacokinetic parameters of ARGX-113 including maximum observed concentration (C_{max}), time of maximum concentration (t_{max}), concentration prior to dosing (C_{trough}), half-life ($t_{1/2,\lambda_z}$), and accumulation ratio (R_{ac}).
- Evaluation of PD markers: total IgG (and subtypes) and anti-AChR antibodies.
- Evaluate the incidence of anti-drug antibodies (ADA) to ARGX-113.
- Exploratory pharmacogenetic assessments in patients who sign a separate pharmacogenetic ICF to examine FcRn polymorphisms.

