14.6 Appendix 6: Sample Size

Assuming MG-ADL scores as a key indicator for efficacy. To detect the difference of 4 points between MG-ADL scores of Active and Placebo with variability ⁽¹⁾ SD=1.80 for active and SD=3.72 for placebo, a sample size of 10 subjects per group would be sufficient to achieve 80% power. Approximately 36 patients will be screened in order to randomize approximately 24 patients (12 patients per treatment arm) to get at least 20 patients who received at least 3 doses of IMP (either ARGX-113 or placebo) and who completed at least 2 weeks of follow-up post last dose. Based on below calculation data of 10 to 12 subjects per group would be sufficient to produce clinically meaningful data for further exploratory analysis. Although this study is exploratory and not statistically powered, descriptive efficacy assessments will be analyzed to assist in designing future studies.

nQuery output:

Two group Satterthwaite t-test of equal means (unequal variances) (equal n's)

	1	2
Test significance level, α	0.050	0.050
1 or 2 sided test?	2	2
Group 1 mean, μ_1	4.300	4.000
Group 2 mean, μ_2	7.900	8.000
Difference in means, $\mu_1 - \mu_2$	-3.600	-4.000
Group 1 standard deviation, σ_1	1.800	1.800
Group 2 standard deviation, σ_2	3.720	3.720
Power (%)	80	80
n per group	12	10

Reference: Howard JF, Barohn RJ, Cutter GR, Freimer M, Juel VC et al. A Randomized, Double-Blind, Placebo-Controlled Phase II Study of Eculizumab in Patients with Refractory Generalized Myasthenia Gravis. Muscle & Nerve. 2013 Jul; 48 (1): 76-84.

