3.3. CHANGES TO ANALYSIS FROM PROTOCOL

As per the protocol, the analysis of change from baseline in the efficacy rating scales is to be performed using Mixed Model Repeated Measures (MMRM) with fixed treatment, baseline score and subject as a random effect. This has been updated in Section 16 of the SAP to use MMRM model including treatment, visit and treatment x visit interaction terms as fixed effects, with baseline and baseline x visit terms as covariates and subject as random effect.

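### The SAP lets the analyst drop baseline x visit from the efficacy model after an optional pre-test with no stated degrees-of-freedom method, so the reported estimates do not come from one fixed model

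*SAP*

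**What the plan says.** Three places in the SAP describe the model for change from baseline in MG-ADL, QMG, MGC and MGQoL15r.

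- **Section 3.3** (changes from the protocol) lists the model "with baseline and baseline x visit terms as covariates and subject as random effect". It mentions no exclusion.
- **Section 15** specifies treatment, visit, treatment x visit, baseline and baseline x visit, and then says: "If the baseline x visit term is found to be not significant then it can be excluded from the model". On the covariance it says: "An unstructured (UN) covariance matrix for the repeated measures within subject will be specified for the analysis". If that does not converge, a simpler matrix such as heterogeneous compound symmetry is to be used.
- **Section 7.1** includes the interaction where appropriate and says: "In case of non-convergence, baseline*visit term will be excluded from the model and/or an appropriate covariance matrix will be used".

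The only threshold that could apply to the pre-test is the default in Section 6.6: "The default significance level will be (5%); confidence intervals will be 95% and all tests will be two-sided, unless otherwise specified". Neither document names a denominator degrees-of-freedom method. The SAP does not say whether the choice is made scale by scale or once for all four, or who makes it.

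On timing, Section 4.3 places the final analysis after database lock, and Protocol 7.8 places unblinding after hard lock.

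**The concern.** Section 15 allows the term to be dropped but does not require it. Two analysts with the same data and the same non-significant test could report different models, and both would comply with the SAP. Section 7.1 adds a separate route to removal and joins it to the covariance change with an and/or, so the order of the two steps is open. The choice falls at a stage when treatment codes are available and treatment is in the model.

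The treatment difference at each visit depends on which model is used, and the standard error and confidence interval take no account of the selection. Protocol Appendix 14.6 says the efficacy results are meant to help design future studies. The estimates and intervals are therefore what the efficacy analysis delivers, and a reader should be able to tell that they came from one planned model.

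The threshold is also unclear. With 24 patients and nine repeated measures under an unstructured covariance, what a 5% test means depends heavily on the degrees-of-freedom method.

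**Working it through.** **The plan's own figure.** Appendix 14.6 gives 10 per group for a 4-point MG-ADL difference (SDs 1.80 and 3.72) and 12 per group for 3.6 points, at 80% power. The noncentral t with Satterthwaite degrees of freedom gives 80.75% at 10 and 80.8% at 12, so both reproduce. Neither document states a size for the baseline x visit test.

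**Inputs for the pre-test.**
- N = 24, 12 per arm (Protocol Appendix 14.6).
- Nine post-baseline efficacy visits: "at Visits 3, 5, 7, 9, 10, 11, 12, 14, and 16 for the following" (Protocol 4.2). The test of equal slopes therefore has q = 9 − 1 = 8 numerator df.
- Unstructured covariance (SAP 15) and a 5% level (SAP 6.6).
- Assumed: complete data and normal scores. The denominator df, d, is not stated, so a range is shown.

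**Size of the test.** With complete data the full model is a separate ANCOVA at each visit, with error df ν = 24 − 3 = 21 (intercept, treatment, baseline). The Wald statistic for equal slopes is a Hotelling T², and under equal slopes

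T² × (ν − q + 1)/(ν q) = T² × 14/168 ~ F(8, 14).

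An uncorrected test compares T²/8 with the 95% point of F(8, d), so

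size = P[F(8, 14) > F₀.₉₅(8, d) × 14/21].

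| Denominator df | F₀.₉₅(8, d) | × 14/21 | Size |
|---|---|---|---|
| 21 (between-within) | 2.42 | 1.614 | 20.7% |
| 168 (21 × 8) | 1.994 | 1.329 | 30.6% |
| 189 (residual, 24 × 9 − 27) | 1.988 | 1.325 | 30.8% |
| 14, exact Hotelling, which Kenward-Roger equals here | 2.699 | not applied; T² × 14/168 used directly | 5.0% |

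Simulation of 4,000 trials per scenario with 21 df gave 21.3% to 21.7%. At N = 20, the protocol's minimum evaluable number, the size is 27.0% (17 df) to 39.7% (residual, 153 df), and 5% with Kenward-Roger.

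**How much the df method changes the model chosen.** When baseline slopes truly differ (simulated from −0.1 to −0.6), the term is kept in 43% (autoregressive correlation) or 69% (compound-symmetric) of trials with 21 df. With the exact test the figures are 16% and 35%.

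**Shift in the estimate.** Assume residual SD 2.5, baseline SD 3, 24 patients and complete data. The standard error of the Visit 16 difference is about 2.5 × √(2/12) = 1.02. The difference between the full-model and common-slope estimates was simulated:

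| Baseline slopes | SD of shift | 95th percentile of absolute shift |
|---|---|---|
| Equal across visits | about 0.2 points | about 0.45 |
| From −0.1 to −0.5 | 0.33 to 0.37 points | about 0.7 to 0.8 |

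For scale, SAP 18 counts a 2-point MG-ADL drop as clinically significant improvement. In a separate simulation with slopes equal or from −0.1 to −0.6, choosing one model over the other changed per-visit p-values by 0.06 to 0.10 on average, and 1.3% to 2.2% of visit comparisons crossed 0.05.

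**Treatment type I error, averaged over visits.** It was 4.9% to 5.0% with the term always kept, and 5.1% to 5.2% with the pre-test applied mechanically. In a further simulation with residual SD 2.5 and baseline SD 3, the smaller p-value was deliberately taken whenever the pre-test was non-significant. The rate was then 5.2% to 5.9%, against 5.0% to 5.4% for the full model in the same runs, an excess of 0.3 to 0.6 points.

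**The case against.** The case for leaving the text alone has real weight.

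- **The direction is benign.** A pre-test that rejects too often keeps the term more often, and keeping the term is the remedy proposed here. This stands: the oversized test is not itself evidence of harm to the treatment comparison.
- **The effect is small.** Type I error moves by less than one percentage point even under deliberate picking, and the estimate typically shifts by a fifth to about a third of a standard error. This stands, within the simulated conditions.
- **The stakes are limited.** Safety is the primary objective. Efficacy is secondary, no confirmatory testing is planned (SAP 7.4), and p-values are descriptive (Protocol 10.4). This stands and limits the severity.
- **Sections 7.1 and 15 need not contradict each other.** A reader might infer that 7.1 allows removal solely for non-convergence. It does not say that. The two sections give two triggers that can coexist. The remaining problem is that neither orders the steps or makes the choice binding.
- **Unblinded, scale-by-scale selection is not written down.** This is correct. Availability of the treatment codes follows from the order of lock, unblinding and analysis. A choice for each scale is only the natural reading.

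The objection does not remove the discretion. An optional model choice made at the analysis stage is what a SAP is meant to exclude, and it can be closed at almost no cost.

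**Conclusion.** The point holds, at minor to moderate severity. SAP 15 makes the efficacy model depend on an optional pre-test at the analysis stage, SAP 7.1 adds an unordered second trigger, and the pre-test's 5% level is not well defined without a degrees-of-freedom method.

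Two stronger readings are not supported. A reader might conclude that the pre-test simply has a true size of 21% to 31%. That range requires an unstructured covariance, 24 patients, complete data and no small-sample correction. The documents do not say which df method will be used, and with Kenward-Roger the size is 5%. The figure does not cover the heterogeneous compound-symmetry fallback, for which nothing was computed. A reader might also conclude that the efficacy analysis is invalid. The simulated error rates do not show that.

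The shift in the estimate rests on assumed SDs (2.5 and 3), correlations and slopes, none of which is in the documents, and on complete normal data.

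**What to change.** 1. Delete the sentence in SAP 15 that allows exclusion on non-significance, and keep baseline x visit in the model for all four scales.
2. Allow removal only for non-convergence, and only after the covariance fallback has been tried. Report each scale where this happens.
3. Reword Section 7.1 to state that order in place of the and/or, so that it agrees with Section 15. Section 3.3, which lists the term without an exclusion, then also agrees.

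Naming the denominator df method (for example Kenward-Roger) would also settle how the remaining tests and intervals are computed.

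The cost is a few lines of SAP text. The statistical downside is up to 8 extra fixed-effect parameters (nine visit-specific slopes in place of one). With complete data the comparison at each visit is then an ANCOVA on 24 − 3 = 21 df, with simulated type I error of 4.9% to 5.0%.
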